Aim 1. To determine differences in glycemic control, as measured by time in range between 80-180 mg/dl (efficacy outcome) and frequency of hypoglycemia (safety outcome), between DexcomG6 CGM and POC BG testing in hospitalized patients with T1D and T2D treated with basal bolus insulin regimen.

All patients with a known history of T1D and T2D admitted to general medicine and surgery units (non-ICU) receiving insulin therapy, will be considered as potential candidates for participation. Patients will be randomized to POC testing (standard of care group) or to Dexcom G6 (CGM group) to guide daily insulin dose adjustment. Patients in the POC testing group will wear blinded CGMs and providers will adjust insulin dose based on POC results before meals and bedtime (current standard of care). Providers in the CGM group will adjust insulin dose based on daily CGM glucose profile information.

Study Diagram:

We will randomize a total of 185 (the first 5 participants will not be included in the analysis but will be used to ensure the technology is working appropriately without any sensor or connectivity issues. If issues are identified, corrections will be made at this time so as to not affect the integrity of the study) male and female subjects >18 years with T1D and T2D treated with basal bolus insulin regimen and with expected hospitalization longer than 3 days. Due to the design of this study, there will be no run-in period. Upon arrival to the emergency department or medical or general surgical wards, subjects will be screened. Patients admitted with acute or chronic medical illnesses, emergency or elective surgical procedures and trauma would be included in the study.

Standard of Care Group: Glucose monitoring by POC testing will be performed before meals and at bedtime. Results will be uploaded in the electronic medical record (EMR) system. The research team together with the PCP team will adjust daily insulin orders based on POC readings (standard of care)^{10,14,43} In addition, patients will wear a 'blinded' CGM (no results will be visualized by patients, nursing staff, PCP or research teams).

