CGM Group: Patients will wear a real-time Dexcom G6 CGM, which provide BG readings every 5 minutes for up to 10 days. In addition, patients will undergo POC testing before meals and bedtime per hospital protocol. Insulin therapy will be titrated based on daily CGM printouts, which will include BG readings, glycemic excursions, hypoglycemia and severe hyperglycemia values throughout the day. Patients will wear a CGM in the current approved insertion site, the abdomen, and in the upper arm, both during hospitalization (up to 10 days).

Primary and Secondary Research Outcomes:

The primary aim is difference between POC testing (standard of care) and CGM in glycemic control (efficacy outcome) and hypoglycemic events (safety outcome) during hospitalization:

- 1) Glycemic control, as measured by time in range between 80-180 mg/dl (efficacy outcome)
- 2) Clinically significant hypoglycemia <54 mg/dl (safety outcome)

Secondary outcomes include differences between groups in any of the following measures:

1. Nocturnal hypoglycemia < 70 mg/dl and < 54 mg/dl (between 22:00 and 06:00)
2. Number of hypoglycemia events (< 70 and 54 mg/dl)
3. Duration or time in hypoglycemia (minutes) during the day and night
4. Frequency and duration of time in hyperglycemia > 250 mg/dl
5. Percentage of BG readings within target BG of 80 and 180 mg/dl
6. Glycemic variability calculated by Standard Deviation, and MAGE
7. Differences in BG by CGM devices placed in the abdomen and upper extremity
8. Number of sensor removal for procedures/imaging, sensors failures, sensors dislodgments

9. After discharge: time in range (TIR), frequency of and time in hypoglycemia (TIHypo), frequency of and time in hyperglycemia (TIHyper), glycemic variability (GV)

Inclusion Criteria:

1. Males and females \geq 18 years admitted to a general medicine or surgical services.
2. Diagnosis of: T1D or T2D receiving insulin therapy during hospital admission.
3. Subjects must have a randomization BG $<$ 400 mg/dL without laboratory evidence of diabetic ketoacidosis (bicarbonate $<$ 18 mEq/L, pH $<$ 7.30, or positive serum or urinary ketones).
4. Patients with expected hospital length-of-stay of 2 or more days

Exclusion Criteria:

1. Patients with acute illness admitted to the ICU or expected to require admission to the ICU.
2. Patients expected to require MRI procedures during hospitalization.

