3. Patients with clinically relevant hepatic disease (diagnosed liver cirrhosis and portal hypertension), corticosteroid therapy (equal to a prednisone dose \geq 5 mg/day), end-stage renal disease (dialysis), or anasarca.
4. Mental condition rendering the subject unable to understand the nature, scope, and possible consequences of the study.
5. Female subjects who are pregnant or breast-feeding at time of enrollment into the study.
6. COVID-19 infection

Subjects who are later found to be COVID-19 positive after enrollment, will be withdrawn from the study. If the infection appears 48 hours after enrollment, it will be documented as a complication as described in the data collection forms.

CGM Data Accuracy analysis:

Interstitial glucose values collected by CGM will be paired with POC BG (closed values within 15 min range). Patients with \geq 2 days of sensor data, and with a minimum of 70% of CGM readings over used days will be included in the comparison analysis. A minimum of approximately 70% of possible CGM readings over used days appears to generate a report that enables optimal analysis and decision-making; standard reporting and visualization of CGM data are important ^{44,45}. CGM metrics will include overall MARD (mean absolute relative difference) and MAD (mean absolute difference), as well as the percentage of sensor values that fall within either 30 mg/dl of the POC testing or 30% glucose concentration. Similar calculations will be performed for 20 mg/dl/20% and 10 mg/dl/10% stratified by glucose values $<$ 70 mg/dl, 70-140 mg/dl, $>$ 140-180 mg/dl and $>$ 180 mg/dl ⁴⁵. The MARD reflects accuracy of the CGM glucose reading compared to the reference POC reading. This is the current standard for assessing accuracy of glucometer readings. Lower MARD indicates smaller differences between the CGM and meter value; a higher MARD value indicates larger differences. A three way and direct head-to-head comparison of data from the abdomen, upper arm and POC BG will be compared.

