CGM – alarms and hypoglycemia protocol. We will use a real-time Dexcom CGM device with a modified transmitter able to store and transmit glucose data to different devices including a notebook/IPAD or computer desk located at the nursing station. **The hypoglycemia alarm** will be set at 80 mg/dl to alert the nursing staff and providers that a patient is at risk of hypoglycemia. If this occurs, the nursing staff will meet patient in the room to assess clinical status and signs/symptoms of hypoglycemia and will perform a POC glucose testing to confirm glucose values. Nursing staff will be instructed to document POC at the time and provide 15 grams of carbohydrates to treat and prevent a serious hypoglycemic event.

Patients in the Standard of Care group will wear a blinded CGM and without alarms, but BG levels will be recorded (in a blinded fashion). If a POCT BG value is $<$ 80 mg/dl, 15 grams of carbohydrates will be given as a preventive measurement to avoid clinically significant hypoglycemia.

An additional CGM alarm will be set up if $BG > 250\text{mg/dL}$ for one (1) hour. The alarms will be set up only for the research team following the participants assigned to real-time intervention. The research physician will determine if treatment changes need to be done and notify the nursing staff of such changes that require immediate attention.

Treatment randomization. Patients will be randomized using a computer-generated randomization table. Treatment randomization/assignment will be coordinated by the statistician [name]. A research person (not actively involved in recruitment) at each institution will follow a computer-generated block randomization table based on glucose levels ($BG \leq 200$ or $BG > 200\text{ mg/dL}$) at randomization.

Recommended Basal Bolus Insulin Protocol.

Patients will be treated with a basal bolus insulin regimen as previously reported ^{12,13}.

During the first day of study enrollment POC BG values will be used to start insulin dosing in both groups.

T1D TREATMENT PROTOCOL

- Patients will be T1D will be treated with basal bolus insulin regimen, given 50% basal (glargine or detemir) and 50% of rapid acting insulin (lispro or aspart) before meals. This will be adjusted at physician's discretion based on the patient's home insulin regimen.

T2D TREATMENT PROTOCOL

Patients T2D Treated with Insulin Prior to Admission

- Discontinue oral antidiabetic drugs on admission.

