We will report baseline characteristics by hospital service (medicine and surgery), diabetes type, and risk factors for hypoglycemia. The rates of incidence of hypoglycemia will be calculated based on the data obtained by CGM and POC. Comparisons will be made with the use of Wilcoxon tests (or Kruskal-Wallis tests) and Chi-square tests (or Fisher's exact test) as appropriate. Multivariate linear regression will be conducted to assess the difference in continuous secondary outcomes between the two groups while other relevant covariates. To be eligible for analysis at least 70% of CGM values need to be available per day, with at least 2 eligible days of data per subject in each study arm (inpatient and outpatient). Glucose patterns will be analyzed based on the Ambulatory Glucose Profile, recently endorsed by an international expert as a standardized approach for CGM interpretation⁴⁴. Hospital glucose values after the first day of insulin treatment will be included in the analysis to allow us to have a full 24-hrs glucose profile and to avoid analyzing day-1 CGM values which may have lower accuracy. For clinical accuracy, CGM and POC BG will be paired and will be plotted in the Clarke Error Grid^{46,47}. Paired CGM and POC BG falling in the Zone A will be defined as "accurate", and in Zone B as "acceptable", with remaining values considered "not acceptable" if falling in Zone C, D, or E.

A total of 180 insulin treated patients will be included in this prospective study. Based on previous studies by our unit, we anticipate that 80% of patients will complete the inpatient and ambulatory arms of the study^{13,48}.

V. Methods and Procedures Applied to Human Subjects:

Potential Risk to Human Subjects

Hypoglycemia. The risk of hypoglycemia in non-ICU patients treated with basal-bolus insulin is between 12%–35%^{14,19,37,49}. In this analysis, hypoglycemia is defined as a BG or IG < 70 mg/dL. Clinical significant hypoglycemia is defined as BG or IG < 56 mg/dL. Severe hypoglycemia is defined as BG or IG < 40 mg/dL.

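### The two length-of-stay entry rules conflict, and the shorter one can admit patients whom the CGM-day rule later excludes from analysis

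*Combined protocol and SAP*

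**What the plan says.** Three places in the combined protocol and SAP bear on this point.

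- **Section III, Aim 1, text under Study Diagram.** The 185 patients to be randomized are described as being "with expected hospitalization longer than 3 days".
- **Section III, Inclusion Criteria, criterion 4.** The entry rule reads "Patients with expected hospital length-of-stay of 2 or more days".
- **Section IV, Statistical Methods.** The analysis rule reads "To be eligible for analysis at least 70% of CGM values need to be available per day, with at least 2 eligible days of data", and it applies to the inpatient and outpatient parts separately. The section also says "Hospital glucose values after the first day of insulin treatment will be included in the analysis". It gives two reasons: "to allow us to have a full 24-hrs glucose profile", and that sensor readings on day 1 may be less accurate.

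The Informed Consent paragraph in section V says that research staff screen against the listed inclusion and exclusion criteria. Criterion 4 is therefore the likely working rule. No passage says so outright, and none withdraws the longer figure.

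**The concern.** A patient expected to stay two to three days satisfies criterion 4 but not the design text. That conflict in an eligibility threshold needs correcting in any case.

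The further problem is that the lower threshold does not fit the plan's own analysis rule. Once the first day is removed, a patient at the criterion 4 minimum may be unable to supply two qualifying days even with a perfect sensor record. Such a patient would be randomized, treated and then left out. Time in range, the efficacy outcome listed in section III, is directly exposed to the extent that it is derived from CGM. The plan describes no sensitivity analysis that would bring the excluded patients back, and it does not say whether the 10% attrition allowance was meant to cover them.

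**Working it through.** **1. The plan's sample size reproduces.** Inputs from section IV: margin 18 mg/dl, SD 45 mg/dl, true difference 0, one-sided two-sample t-test, 80% power. Alpha is not stated.

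- n per arm = 2 × (z for alpha + z for power)² × (SD/margin)². With one-sided alpha 0.05: 2 × (1.645 + 0.842)² × (45/18)² = 77.3, so 78, the plan's figure.
- With one-sided alpha 0.025 the result is 99, so 0.05 is inferred.
- Noncentral t power is 0.796 at 77 per arm, 0.800 at 78, 0.813 at 81 and 0.848 at 90.
- Attrition: 78/0.90 = 86.7, so 87. The plan's 90 is a little more generous.

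**2. Whole-day count.** Analysable inpatient days = days of stay − 1, against a minimum of 2.

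- 2-day stay: 2 − 1 = 1, fails.
- 3-day stay: 3 − 1 = 2, just passes if both days reach 70%.
- More than 3 days: more than 2, passes.

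**3. The count in hours depends on definitions the plan does not give.** The sensor reads every 5 minutes, so a day holds 288 readings, and 70% is 201.6 readings or 16.8 h. Assume a complete record and a clock that starts at enrolment at hour h.

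- *24-hour periods, day 1 dropped, 288 readings expected.* Needs 24 + 24 + 16.8 = 64.8 h. A 48-h record never passes.
- *Calendar days, enrolment date dropped, 288 readings expected.* Needs (24 − h) + 24 + 16.8 = 64.8 − h hours. A 48-h record passes only for starts at or after 16:48.
- *Calendar days, enrolment date dropped, part days judged on the readings possible that day.* A 48-h record passes except for a midnight start.
- *First 24 h dropped, then calendar days with 288 readings expected.* A 48-h record leaves 24 h. Two qualifying days need 2 × 16.8 = 33.6 h, so it never passes. A 72-h record leaves 24 − h, 24 and h hours. It fails when both part days fall short of 16.8 h, that is, for starts between 07:12 and 16:48. For example, a 10:00 start leaves 14 h (58%), 24 h (100%) and 10 h (42%), which is one qualifying day. For starts after 07:12 the first part day fails, so the record must reach 24 + (24 − h) + 24 + 16.8 = 88.8 − h hours. This is up to 81.6 h, at h = 7.2.

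These are clock-time conditions for a record of exactly the stated length. They are not proportions of patients.

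**4. Slack in the sample size**, if the CGM rule also decides who contributes mean daily glucose.

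- All causes of loss together: 90 − 78 = 12 per arm (12/90 = 13.3%).
- After the planned 10% attrition: 90 × 0.90 = 81, and 81 − 78 = 3 per arm (3/81 = 3.7%).

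**The case against.** The strongest reply is that criterion 4 is a floor on the *expected* stay. Many patients will stay longer, and some readings of a day let a 48-h stay through. Insulin treatment may also begin before enrolment, since criterion 2 requires "T1D or T2D receiving insulin therapy during hospital admission", so the dropped day could precede the sensor record. All of this can happen, and it rules out saying that every patient admitted under criterion 4 with a short expected stay is lost.

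It does not remove the mismatch. The insulin protocol says "During the first day of study enrollment POC BG values will be used to start insulin dosing in both groups", which ties the start to enrolment. One stated reason for dropping day 1 concerns sensor accuracy, so insulin begun earlier does not clearly release the first sensor day. For the same reason it is strained to count an unanalysed day towards the two. The more lenient phrase "A minimum of approximately 70% of possible CGM readings over used days" belongs to the CGM accuracy analysis and does not settle the rule in section IV.

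It is also fair to say that the numbered criteria are the likely screening rule, so sites may not be confused in practice. But that makes the shorter threshold the operative one, and it is the one that fits the analysis rule poorly.

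A reader might go further in three ways that the documents do not support.

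- *The trial is underpowered.* There are no length-of-stay data, and the SD of 45 mg/dl is the plan's upper bound. The 80% completion figure in section IV (72 of 90 per arm, power 0.771) covers the inpatient and post-discharge parts together, so it is not an inpatient loss rate.
- *The exclusions bias the comparison.* Nothing indicates that short stays will differ between arms.
- *More than 3 days is safe however days are counted.* The last reading in step 3 of the working shows otherwise.

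**Conclusion.** The point stands. Two entry thresholds conflict in current text. In whole days the lower one supplies one analysable inpatient day where the analysis rule needs two. The plan can therefore randomize patients whom its own rule then excludes for a short stay.

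How many is unknown. The loss that can be absorbed is 12 per arm from all causes, or 3 per arm beyond the planned attrition. Both figures rest on one-sided alpha 0.05, inferred from the stated 78, and on the assumption that the CGM rule governs mean daily glucose. Section IV names mean daily glucose as part of the primary endpoint without giving its inpatient source. The conclusion is a mismatch to correct, with no demonstrated loss of power and no demonstrated bias.

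**What to change.** 1. Reconcile the design text and criterion 4 to one expected stay, counted from randomization.
2. Fix how a day and a part day are counted, when the clock starts and how day 1 is treated. Then check the chosen stay against that rule. Do not state that 72 h suffices whatever the definition.
3. State whether the 10% attrition includes patients who fail the CGM-day rule, and whether that rule applies to mean daily glucose.
4. Keep the 70%, two-day set. Add a sensitivity analysis of all randomized patients, after the first 5 technology-check patients, who have any CGM values after day 1. This wider set still depends on length of stay and should be described that way.
5. Report exclusions and reasons by arm, including patients with no CGM values. An expected stay does not guarantee the actual one, so this is needed whichever threshold is kept.

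The cost is one wording amendment and a few SAP sentences, with no new data collection. The drawbacks are possibly slower enrolment if the longer stay is kept, of a size the documents do not allow one to estimate, and noisier values from short records in the wider set.

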- Patients with admission HbA1c < 7.5% will be discharged on their preadmission antidiabetic regimen.
- Patients on oral agents prior to admission with an HbA1c between 7.5% and <10% will be discharged on oral agents plus basal insulin (glargine, detemir, degludec) at 50% of the daily hospital dose.
- Patients on oral agents prior to admission with an admission A1C ≥ 10% will be discharged on their oral agents plus basal insulin at 80% of daily hospital dose.
- Patients on oral agents plus basal insulin (NPH, glargine, detemir) prior to admission with an admission A1C between 7.5% and <10% will be discharged on their oral agents plus basal insulin at 50% of daily hospital dose.
- Patients on oral agents plus basal insulin (NPH, glargine, detemir) prior to admission with an admission A1C ≥ 10% will be discharged on their oral agents plus basal insulin at 80% of daily hospital dose.
- Patients treated with basal bolus regimen prior to admission will be discharged on 80% of their preadmission TDD with basal insulin once daily and rapid-acting insulin before meals.

Follow-up Care:

- Duration of post discharge study: ~10 days (participant can return sooner or later depending on his/her schedule)
- New CGM (blinded) sensor will be placed (abdomen or arm at investigator's discretion) before discharge. If primary care team is planning to discharge over the weekend: participants will get new blinded sensor on Friday evening prior to discharge. The real time CGM will be left in the abdomen to continue to monitor during hospital stay. Participant will be asked to return on the following business working day to remove real time CGM. Blinded sensor (placed before discharge) will be removed at 10 day follow up visit after discharge.
- Patients will be asked to continue checking their blood glucose by regular POCT and will return to the outpatient clinic visit at 10 days after discharge (sooner or later depending on participant's availability and schedule).

The following information will be collected after discharge:

1. Glycemic control:
 - a. Mean daily blood glucose by CGM and POC testing
 - b. Time in range (80-180 mg/dl)
 - c. Frequency of overall clinically significant hypoglycemia (<54 mg/dl) and severe hyperglycemia (>250 mg/dl).
 - d. Nocturnal hypoglycemia < 70 mg/dl and < 54 mg/dl (between 22:00 and 06:00)
 - e. Duration or time in hypoglycemia (minutes) during the day and night
 - f. Frequency and duration of time in hyperglycemia > 240 mg/dl

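### Fingerstick tests triggered by one sensor's low alarm enter the CGM accuracy analysis unseparated and tilt the abdomen-versus-arm comparison, mainly at 70-140 mg/dl

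*Combined protocol and SAP*

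**What the plan says.** The section on CGM data accuracy sets the pairing rule: "Interstitial glucose values collected by CGM will be paired with POC BG (closed values within 15 min range". It then lists the measures: "CGM metrics will include overall MARD (mean absolute relative difference) and MAD (mean absolute difference", plus agreement within 30, 20 and 10 mg/dl or percent. "Similar calculations will be performed for 20 mg/dl/20% and 10 mg/dl/10% stratified by glucose values" follows, with cut points at 70, 140 and 180 mg/dl. The section does not say whether the POC or the CGM value assigns a pair to its stratum. It closes with the site comparison: "A three way and direct head-to-head comparison of data from the abdomen, upper arm and POC BG will be compared". Section IV adds a Clarke error grid on paired values.

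Two kinds of POC test arise in the CGM group:

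- **Scheduled.** The CGM Group paragraph says "patients will undergo POC testing before meals and bedtime per hospital protocol".
- **Alarm-triggered.** The alarm section says the hypoglycemia alarm "will be set at 80 mg/dl to alert the nursing staff and providers that a patient is at risk of hypoglycemia". When it sounds, nursing staff "will perform a POC glucose testing to confirm glucose values" and record the result. Section V repeats the alarm-triggered test and adds tests prompted by symptoms.

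The CGM Group paragraph places sensors on both the abdomen and the upper arm. Only the weekend-discharge instruction under Follow-up Care indicates which one is real-time: "The real time CGM will be left in the abdomen". Standard-of-care patients wear a blinded sensor without alarms.

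**The concern.** A scheduled test is taken whatever the sensors show, so it is a fair reference for both. An alarm-triggered test is taken only because one sensor fell below 80 mg/dl. That sensor falls below 80 partly because glucose is low and partly because its own error is negative at that moment. Conditioning on the alarm selects negative errors in the alarming sensor. It does not select the other sensor's errors, except so far as the two are correlated.

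No stated restriction removes this. The rules on minimum days, 70% of readings and dropping the first day concern how much sensor data there is, not why a POC value exists. At stake is whether the trial reports a difference in accuracy between body sites that comes from the testing rule rather than the sites, and whether the real-time group's accuracy near the alarm threshold is misdescribed.

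**Working it through.** **The plan's own figure.** The documents give no power or precision figure for the accuracy analysis. Their one calculation concerns mean daily BG: margin 18 mg/dl, SD 45 mg/dl, 80% power, and one-sided 0.05 (alpha is not stated but is implied). 2 × (1.645 + 0.842)² × (45/18)² = 77.3, or 78 per group as stated. 78/0.9 = 86.7, which the plan rounds up to 90. Alarm-triggered pairs do not enter it.

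**Mechanism.** Let A be the alarming sensor, B the other, e their relative errors and ρ the correlation of those errors. Given A < 80, the mean of e_A is negative. The mean of e_B is about ρ times that, so it is near zero when ρ = 0.

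**Simulation.** Two equally accurate sensors were simulated with four scheduled POC tests a day and one extra test each time A crosses below 80 mg/dl. From the documents: the 80 mg/dl threshold, the test schedule and the strata. Assumed, because the documents give no values: sensor error CV 10-16%, POC CV 5%, median glucose 150-190 mg/dl, interstitial lag absent or present, POC test 0-10 minutes after the alarm, ρ from 0 to 0.5. 20/20 was taken as within 20 mg/dl below 100 mg/dl and within 20% otherwise, and POC defined the strata. Seven of the 12 scenarios (entries are A / B, in %):

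| Scenario | Alarm share of pairs | Overall MARD, scheduled | Overall MARD, all | 70-140 MARD, scheduled | 70-140 MARD, all | 70-140 20/20, all | <70 MARD, all | <70 20/20, all |
|---|---|---|---|---|---|---|---|---|
| CV 10% | 11.8 | 9.5 / 9.5 | 9.7 / 9.5 | 9.6 / 9.6 | 10.1 / 9.5 | 89.6 / 92.1 | 11.4 / 11.9 | 98.3 / 96.5 |
| CV 13% | 14.2 | 11.6 / 11.6 | 12.1 / 11.6 | 11.8 / 11.8 | 12.9 / 11.7 | 80.0 / 84.8 | 13.5 / 14.7 | 95.4 / 91.4 |
| CV 16% | 18.6 | 13.7 / 13.8 | 14.9 / 13.8 | 13.9 / 14.1 | 16.0 / 14.0 | 68.6 / 77.0 | 14.8 / 17.6 | 91.6 / 84.6 |
| CV 13%, ρ = 0.5 | 14.3 | 11.6 / 11.6 | 12.1 / 11.8 | 11.8 / 11.8 | 12.9 / 12.0 | 79.9 / 83.7 | 13.4 / 14.3 | 96.0 / 92.0 |
| CV 13%, no delay | 14.2 | 11.6 / 11.6 | 12.1 / 11.7 | 11.8 / 11.8 | 12.7 / 11.9 | 79.8 / 84.9 | 16.8 / 15.7 | 94.5 / 89.3 |
| CV 13%, median 190 | 8.1 | 11.6 / 11.5 | 12.0 / 11.6 | 11.9 / 11.8 | 13.1 / 11.7 | 78.9 / 84.5 | 12.5 / 14.8 | 96.6 / 89.6 |
| CV 13%, median 150 | 23.8 | 11.6 / 11.6 | 12.2 / 11.6 | 11.7 / 11.6 | 12.7 / 11.5 | 81.1 / 86.0 | 13.3 / 14.8 | 95.4 / 90.8 |

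**Bias in the alarm pairs alone (CV 13%).** There were 100,000 scheduled pairs and 116,590 in all, so 16,590 alarm pairs. Mean signed difference for A: (116,590 × (-1.6) - 100,000 × 0.2) / 16,590 = -12.4 mg/dl. For B: (116,590 × 0.0 - 100,000 × 0.1) / 16,590 = -0.6 mg/dl. Rounding of the inputs allows about ±0.7 on each. With ρ = 0.5 the same steps give -12.6 and -7.1 mg/dl, as the mechanism predicts.

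**Where the alarm pairs fall (CV 13%).** At 70-140: 43,330 - 28,472 = 14,858, or 90% of alarm pairs. Below 70: 2,081 - 548 = 1,533, or 9%. These few nevertheless form 1,533/2,081 = 74% of the <70 stratum.

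**Ranges over all 12 scenarios, all pairs.**

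- Overall: MARD for A 0.2-1.4 points worse.
- 70-140 mg/dl: MARD 0.5-2.8 points worse, 20/20 agreement 2.5-11.3 points lower.
- POC <70 mg/dl: MARD from 2.8 points better to 2.1 worse; 20/20 higher for A throughout, by 1.5-7.8 points, because lows that A misses trigger no test.
- Stratum set by each sensor's own reading below 70: MARD for A worse in 4 of the 5 scenarios run.

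A second set of 12 scenarios (CV 10-13%, median 170-180 mg/dl) gave overall MARD gaps of only 0.0-0.4 points. At POC <70 the alarming sensor's MARD was worse in 10 of 12, but its 20/20 agreement was better in 9 of 12.

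**The case against.** A reader might infer that low-range accuracy is biased against the abdomen. The results do not support that. Below 70 mg/dl the direction changes with the metric and with the stratum definition, which the plan leaves open.

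A reader might also infer that secondary outcome 7 must show a false site difference. That outcome is a difference in glucose between sites. It can be computed from simultaneous sensor readings with no POC reference, and is then untouched.

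Three further limits stand. First, inclusion of the alarm-triggered tests is read from the absence of any exclusion. Second, only the weekend-discharge instruction places the real-time sensor in the abdomen; if the arm sensor alarms instead, the bias moves to the arm. Third, control-arm pairs carry no alarms, so pooling them dilutes the accuracy metrics.

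The effect may also sit near the low end. Section V expects about 10% of inpatients to have hypoglycemia and cites 12-35%. Scenarios in which 9-25% of patients were ever truly below 70 mg/dl gave about 0.9-2.1 alarms per patient.

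One could instead report results with and without alarm pairs. That would expose the problem, but the plan would still need to say which result is the main one.

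**Conclusion.** The concern holds for the abdomen/arm/POC comparison and for the real-time group's accuracy metrics and error grid. Followed as written, the plan makes two equally accurate sites look different, mainly at 70-140 mg/dl and against the alarming sensor. Across all the runs, MARD there is about 0.2-2.8 points worse and 20/20 agreement about 1-11 points lower. The overall MARD effect is about 0-1.4 points. Below 70 mg/dl there is distortion but no fixed direction; a result that flatters the alarming sensor there would be no safer, since it can hide missed lows.

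These sizes rest on assumed sensor and POC error, glucose level, lag and between-site correlation. The mechanism rests only on the plan's testing and pairing rules. The primary outcomes and the sample size are unaffected. This is a worthwhile, inexpensive refinement, not a threat to the trial's main conclusions.

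**What to change.** In the accuracy section and Section IV:

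- Base the main MARD, MAD, 10/20/30 agreement, error grid and site comparison on scheduled (pre-meal and bedtime) POC tests.
- Record the reason for each POC test, and report alarm- and symptom-triggered pairs separately.
- State that the POC value defines the strata, and name the site of the alarming sensor.
- Give intervals by patient-level cluster bootstrap, since each patient contributes many pairs.

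With scheduled pairs only, the gaps between equally accurate sensors in the table are at most 0.2 MARD points, both overall and at 70-140 mg/dl.

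The change is to analysis wording and data labelling; no clinical procedure changes. The price is precision below 70 mg/dl. In the CV 13% scenario, 548 of 2,081 such pairs remain, so intervals there would be about √(2,081/548) = 1.9 times as wide if pairs were independent. The triggered pairs are still reported, so no data are lost.

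### The plan filters CGM accuracy on record completeness, and arguably on day 1, with no all-pairs result, so accuracy may be overstated for the wear time clinicians acted on

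*Combined protocol and SAP*

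**What the plan says.** Under CGM Data Accuracy analysis (Section III), sensor values are paired with POC values no more than 15 minutes apart. The next sentence sets the analysis population: at least 2 days of sensor data are required, and patients with a "minimum of 70% of CGM readings over used days will be included in the comparison analysis". The reason given is that roughly 70% completeness "appears to generate a report that enables optimal analysis and decision-making". The section then lists the measures: MARD, MAD, and agreement within 30, 20 and 10 mg/dl or percent.

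Section IV, Statistical Methods, has its own eligibility rule. It asks for 70% of values on each day and at least 2 eligible days per subject, in both the inpatient and the outpatient part. Hospital values enter the analysis only after the first day of insulin treatment. Two reasons are given: to have a full 24-hour profile, and "to avoid analyzing day-1 CGM values which may have lower accuracy". The next sentence introduces the Clarke Error Grid.

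Neither section plans an accuracy analysis without these filters. Secondary outcome 8 counts sensor problems separately: "Number of sensor removal for procedures/imaging, sensors failures, sensors dislodgments".

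**The concern.** An accuracy pair needs one sensor reading and one POC value at about the same time. It does not need a complete record. A completeness threshold makes sense for time in range, where gaps distort the summary. Applied to pairs, it discards every valid pair from an excluded patient for a reason unrelated to whether the pair is valid.

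The day-1 rule raises a sharper problem, because one of its reasons is accuracy itself. If it governs the error grid and MARD, readings are set aside because they may be inaccurate, and the device is then judged on what is left.

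The readings at issue are not idle in the CGM group. The alarm "will be set at 80 mg/dl to alert the nursing staff and providers that a patient is at risk of hypoglycemia", with no delay stated for day 1. Insulin is adjusted from the previous 24-hour profile, so the first such adjustment draws on day-1 readings. The supplemental scale uses the CGM value at the time of dosing, again with no stated day-1 exception. The protocol's introduction suggests that CGM could take the place of finger-stick testing in insulin-treated inpatients. Evidence for that should cover the readings clinicians used.

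**Working it through.** The plan states no expected MARD, accuracy target, day-1 error or excluded share, so there is no figure to reproduce. What follows is bounding arithmetic on stated assumptions.

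**Effect of dropping day 1.** Let f be the share of pairs that fall on day 1, and e the number of points by which day-1 MARD exceeds later MARD.

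- MARD over all pairs = (1 − f) × later MARD + f × (later MARD + e) = later MARD + f × e.
- MARD without day 1 = later MARD.
- So dropping day 1 lowers the reported figure by f × e.

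With d hospital days and equal numbers of pairs per day (POC tests are scheduled before meals and at bedtime), f = 1/d. Three days is the shortest stay that leaves two days after day 1, and ten days is the maximum sensor wear. The values of e are assumptions.

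| Hospital days | f | e = 0 | e = 1 | e = 3 | e = 5 |
|---|---|---|---|---|---|
| 3 | 33% | 0 | 0.33 | 1.0 | 1.67 |
| 5 | 20% | 0 | 0.20 | 0.6 | 1.0 |
| 7 | 14% | 0 | 0.14 | 0.43 | 0.71 |
| 10 | 10% | 0 | 0.10 | 0.3 | 0.5 |

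If day 1 is a partial day with fewer tests, f is smaller and so is the effect.

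**Effect of the 2-day/70% rule.** The same formula applies, with q the share of pairs lost. Assume q runs from 5% to 20%, and that the lost pairs have MARD anywhere from 2 points better to 5 points worse than the kept ones.

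- Lost pairs better: 0.20 × (−2) = −0.4, so reported MARD is 0.4 points too high.
- Lost pairs worse: 0.20 × 5 = 1.0, so reported MARD is 1.0 point too low.

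The sign is not fixed.

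**How strict the threshold is.** One reading every 5 minutes gives 24 × 60 / 5 = 288 a day. Then 0.70 × 288 = 201.6, about 202 readings, and 0.30 × 24 = 7.2 hours may be missing. The threshold is loose.

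**Short stays.** Inclusion criterion 4 allows an expected stay of 2 days, although the Study Diagram text expects more than 3. If two eligible days are needed after day 1 is removed, a 2-day stay leaves 2 − 1 = 1 day and contributes no inpatient accuracy pairs.

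**Consistency of the rule.** The accuracy section judges 70% across all the days used, and Section IV judges it day by day. A patient with one poor day and several full ones keeps every day under the first rule and loses the poor day under the second. The accuracy set is therefore not uniquely defined.

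**The case against.** The strongest reply is that the day-1 rule is never expressly attached to the accuracy measures. The accuracy section has no day-1 exclusion, Section IV does not mention MARD or MAD, and its paragraph is mainly about outcome comparisons. The first reason it gives, a full 24-hour profile, has nothing to do with accuracy. This stands: applying the rule to the error grid is a reading of the text, and applying it to MARD is a further step. But nothing excludes that reading either.

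A reader might go further and infer that the filters confine the analysis to the sensors' best-performing time, or that they remove all pairs from sensors that failed. The documents do not support this. The rule in the accuracy section works by patient, so someone whose sensor failed or was replaced after two days can remain in with those pairs. The day-1 exclusion is tied to hospital values and the first day of insulin treatment, not to sensor age. Late wear, the first day of a replacement sensor and the first day after discharge are not excluded by it.

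Nor do the documents show that the completeness rule favours the device. Readings can be missing because of discharge, imaging or dislodgment, and nothing links these to poor agreement with POC.

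Some of the clinical exposure is also mitigated. The alarms section asks nurses to confirm an alarm with a POC test, and POC values start insulin dosing on the first day in both groups. Neither safeguard covers the 24-hour profile or the supplemental scale.

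Finally, MARD and the error grid are not among the listed primary or secondary outcomes, and sensor failures are counted separately. That limits the stakes, but a count of failures does not show how those sensors read beforehand.

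**Conclusion.** The concern holds in a limited form. The accuracy analysis carries a completeness filter whose stated reason does not fit paired data. Section IV can be read as also removing day 1, partly on grounds of accuracy, and no unfiltered result is planned. On the plan's own premise that day-1 values may be less accurate, that reading would make the device look better than it was over the whole period of use.

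The size rests on assumptions. With day-1 MARD 0 to 5 points worse and equal pairs per day, the shift is 0 to 1.7 points at 3 hospital days and 0 to 0.5 points at 10. For the 2-day/70% rule alone, no direction can be claimed. The randomised comparison of glycemic control and hypoglycemia is not affected by this point.

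**What to change.** State in both the accuracy section and Section IV that MARD, MAD, the agreement rates and the error grid use every CGM-POC pair within 15 minutes from every sensor worn, day 1 included. Show day 1 against later days, and say whether day 1 is counted from sensor insertion or from the start of insulin treatment. Report the filtered result alongside.

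Keep the 2-day/70% rule for time in range and the other summary measures, and choose one definition of it: across the days used, or on each day.

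The cost is a few sentences and one extra table, from data already being collected. The only downside is that the reported MARD may be slightly less favourable.
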